9.7.1.12 Laboratory Values

Summary statistics for changes from baseline and the incidence of treatment emergent abnormal values in coagulation measurements at 1 hour post drug administration will be provided.

9.7.1.13 Physical Examination, Pelvic Examination, and Vital Signs

By-subject listings will be provided for physical examination and pelvic examination. Summary statistics for change from baseline and incidence of potentially clinically significant results in vital signs will be provided.

9.7.1.14 Efficacy Analyses

All SPID endpoints will be calculated using Simpson's trapezoidal rule. SPID will be calculated as follows, where n is the total number of time points within the time period with non-missing imputed PID values:

If multiple scores are recorded at the same date and time, the most conservative PI scores (highest) will be used.

Primary Efficacy Analyses

The primary efficacy analyses will be performed on the intent-to-treat set. As a sensitivity analysis, the primary efficacy analysis will also be performed on the PP set. Primary efficacy analyses will also be conducted on the per protocol set, which will include all subjects in the ITT set who sufficiently comply with the protocol.

The primary efficacy endpoint will be compared between the URG101 group and the lidocaine, heparin, and placebo groups using an analysis of covariance model including factors for site and randomized treatment assignment; baseline pain will be added to the model as a covariate. Pairwise comparisons of least squares means between URG 101 and the two active treatment arms, as well as the placebo arm, will be performed. The probability values will be derived using the contrast statement from the model. If the p-value associated with these comparisons is < 0.05 in favor of URG101, the primary aim of the trial will be confirmed.

Sites with small numbers of patients enrolled may be pooled for analysis. The method used to determine pooling will be specified in the statistical analysis plan and any pooling will be finalized and documented prior to database lock and unblinding.

Secondary Efficacy Analyses

Analyses of the secondary endpoints relating to changes in the pain and urgency NRS will be performed using analysis of covariance models similar to those used for the primary efficacy endpoint. The ITT set will be used. Nonparametric methodology in exploratory analyses may be used to supplement the parametric analyses.

Treatment differences based on the PORIS questionnaire, Question 3, will be analyzed by pairwise Cochran-Mantel-Haenszel Tests based on $\geq 50\%$ improvement of symptoms.

Time to first pain medication use will be analyzed using Kaplan-Meier methodolgy. Log-rank tests will be used to compare the treament groups.

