Statistical Methods:	
Sample Size Estimate Sample size estimates were based on a pilot trial of heparin-lidocaine versus lidocaine alone and a prior two-arm study of URG101 versus placebo. The primary efficacy endpoint is SPID-12. The sample size calculation is based on a one-way analysis of variance, comparing SPID-12 from four treatment groups. A target sample size of 180 subjects to be allocated unequally among the four treatment groups as follows: URG101:placebo:lidocaine: heparin at 2:1:2:1 (60 subjects per group and 30 subjects per group). This sample size is sufficient to achieve 90% power to detect a difference between the URG101 and lidocaine groups assuming a treatment effect size of 0.60. The study will also have 90% power to detect a difference between the URG101 and each of the placebo and heparin groups assuming an effect size for these comparisons of 0.75. Once 90 subjects have been enrolled, a blinded interim analysis will take place; and, if required, the number of subjects for the study increased to a maximum of 300 subjects.
 
Description of Analysis Sets: All analyses of the efficacy of URG101 will be performed on the ITT set, which will include all randomized subjects from the investigative phase of the study who receive study drug. These efficacy analyses will compare the treatment groups on the basis of randomized treatment, regardless of the treatment actually received. Primary efficacy and key secondary efficacy analyses will also be conducted on a per protocol set, which will include all subjects in the ITT set who sufficiently comply with the protocol.
 
Safety analyses will be based on the safety analysis set which will include all subjects who receive at least one dose of study drug and have at least one post dose safety assessment in both phases of the study. Safety summaries will be produced based on study treatment actually received.

CLINICAL PROTOCOL SYNOPSIS (continued)

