7.5.2 Rationale for Single Dose

The Urogen Study URG101-101 revealed a 51% placebo response rate. This was seen throughout the study, with the exception of one study site. This site enrolled subjects with severe IC/BPS, where the placebo response was 20% in keeping with prior studies with subjects with severe disease.

There is currently no effective therapy to relieve these intense symptom flares.

It is proposed, therefore, to perform a single-dose study to document the effectiveness of URG101 in relieving the intense flare in subjects with IC.

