9.5.1.9 Bladder Pain and Urgency 11-Point Numerical Rating Scales (NRS)

As part of screening, subjects will be asked to fill out two sets of the 11-point bladder pain NRS and the 11-point urgency NRS, one at screening and one 15 minutes (± 5 minutes) after voiding just prior to study drug administration. There is no minimum score requirement for the urgency NRS scales for patients to enter the study. For the Pain NRS, both the screening and [REDACTED] pain NRS requires a score of ≥ 5.0 to enter the trial and receive study drug.

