9.7.1 Statistical and Analytical Plans

The statistical analyses of study data are described in this section. All hypothesis tests will be 2-sided and will use an alpha level of 0.05. Additional details of the analytical plan will be provided in the SAP, which will be finalized before database lock.

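### The primary ANCOVA adjusts for one pre-dose pain score and leaves out the screening pain score and PUF score the protocol already collects: a cheap, unbiased gain in precision, probably small

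*Combined protocol and SAP*

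**What the plan says.** Section 9.7.1.14 compares SPID-12 between URG101 and each other arm with an analysis of covariance that has site and treatment as factors, and "baseline pain will be added to the model as a covariate". The synopsis lists treatment and baseline pain and does not mention site. Section 9.4.1 defines baseline pain and urgency as the NRS scores taken about 15 minutes after voiding, just before dosing.

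Two other severity measures precede dosing. Section 9.5.1.9 says that "subjects will be asked to fill out two sets of the 11-point bladder pain NRS", one at screening and one just before dosing, and requires at least 5 on both pain scores. Sections 9.3.1 and 9.5.1.8 require a PUF score of at least 15 and below 30. Neither the screening NRS nor the PUF score is named in the primary model.

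The pain and urgency secondary endpoints "will be performed using analysis of covariance models similar to those used for the primary efficacy endpoint"; no urgency covariate is named. Section 9.7 defers further detail to a separate SAP, which is not part of the text available here.

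**The concern.** One 0-to-10 rating, cut off below at 5, is a noisy measure of a subject's pre-treatment pain. A second rating, and a questionnaire on usual symptoms, may carry information about later pain that the single rating misses. Any part of the SPID-12 variance they explain beyond the pre-dose score would come out of the residual. That would tighten all three primary comparisons with no further data collection. Section 9.2 says that recruitment in this population is difficult, so precision obtained without more subjects has value. The matter at stake is efficiency, not the validity of the test.

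**Working it through.** **1. The plan's own power.** Inputs: "All hypothesis tests will be 2-sided and will use an alpha level of 0.05" (Section 9.7.1); 60, 30, 60 and 30 subjects for URG101, placebo, lidocaine and heparin (synopsis). The synopsis states: "This sample size is sufficient to achieve 90% power to detect a difference between the URG101 and lidocaine groups". The standardised effect behind that claim is 0.60. For placebo and heparin it claims 90% power, "assuming an effect size for these comparisons of 0.75". Section 9.7.3 bases the size on a one-way analysis of variance, so no covariate gain is credited.

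Power comes from the noncentral t distribution with noncentrality δ/√(1/n₁ + 1/n₂) and 180 − 4 = 176 degrees of freedom (two-sided critical value 1.974).

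- URG101 v lidocaine: 0.60/√(1/60 + 1/60) = 0.60/0.1826 = 3.286, power 90.5%.
- URG101 v placebo or heparin: 0.75/√(1/60 + 1/30) = 0.75/0.2236 = 3.354, power 91.6%.

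Both agree with the stated 90%.

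**2. What a second pain score adds.** SPID-12 is a weighted sum of (pre-dose pain − later pain). With pre-dose pain in the model, the residual variance is therefore that of the weighted post-dose pain given pre-dose pain. Let r be the correlation of pre-dose pain with post-dose pain, s that of screening pain with post-dose pain, and ρ the correlation between the two pre-dose scores. Adding the screening score cuts the residual variance by the fraction

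p = (s − ρr)² / [(1 − ρ²)(1 − r²)],

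and multiplies the effective sample size by 1/(1 − p). The documents give none of r, s or ρ. Assumed ranges: r 0.3 to 0.5, ρ 0.4 to 0.7.

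| Assumed s | Fall in residual variance |
|---|---|
| s = r | 1.7% to 14.3% |
| s = 0.8r | 0.2% to 6.3% |
| s = 0.7r | 0% to 3.6% |
| s = ρr | 0% |

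Example for the top row: r = 0.5, ρ = 0.4 gives (0.5 − 0.2)²/(0.84 × 0.75) = 0.09/0.63 = 14.3%.

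**3. Allowing for the entry cut-off.** A simulation used integer scores (assumed mean 6, SD 2), both pre-dose scores at least 5, eight post-dose scores, and s = r throughout. In five of seven settings (ρ 0.5 to 0.8, r 0.2 to 0.5) the residual variance fell by 1.5% to 7.1%. When r was set equal to ρ, it fell by 10.2% (both 0.3) and 18.9% (both 0.5). The cut-off reduced the gain in every setting. PUF was not simulated.

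**4. In power, at the planned effects.** A gain g in effective sample size multiplies the noncentrality by √g.

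| Gain in effective N | 60 v 60 at 0.60 | 60 v 30 at 0.75 |
|---|---|---|
| none | 90.5% | 91.6% |
| 3% | 91.3% | 92.3% |
| 4.5% | 91.6% | 92.6% |

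For 3%: 3.286 × √1.03 = 3.335. This takes the effect sizes as expressed in residual SDs of the model as planned.

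**5. The cost if the extra covariates explain nothing.** Going from 175 to 173 degrees of freedom changes power at 0.60 by less than 0.01 percentage point.

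**The case against.** Baseline-adjusted ANCOVA is a standard and valid primary model, and the sample size does not rely on any covariate. That stands. A reader might infer that the trial is underpowered or its comparison biased without the extra covariates; step 1 and randomization rule out both.

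The equal-correlation case is also favourable. A score taken up to a week earlier may well predict less than one taken minutes before dosing, and at s = ρr the gain is nil. The entry limits on NRS and PUF weaken both candidates further. This stands too, and it is why the likely size is given as small.

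A reader might take Section 7.5.2 as proof that severity predicts outcome: an earlier study had a 51% placebo response, with one exception, "This site enrolled subjects with severe IC/BPS, where the placebo response was 20" per cent. That is a contrast between sites, not in NRS, PUF or SPID-12, and site is already a factor in Section 9.7.1.14. It is suggestive only.

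Nor do the documents establish that every subject has two distinct pain scores. The synopsis and Sections 9.1 and 9.5.1 combine the assessments of both visits when screening and dosing fall on one day. Section 9.5.1.9 still lists two sets, but does not say what a same-day subject records. This calls for a rule; it does not defeat the point.

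Finally, the secondary-endpoint wording could be read as adjusting urgency for baseline pain. The models are called similar, not identical, and Section 9.4.1 defines a baseline urgency score, so the text needs clarifying rather than correcting. The separate SAP may settle some of this, but the protocol already names the covariate and should agree with it.

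**Conclusion.** The point holds as an efficiency improvement. The primary model omits two pre-dose measures that the protocol requires for entry. Including them cannot bias the randomized comparison and costs almost nothing.

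The omission is certain; the size of the gain is not. Under the assumed correlations, the fall in residual variance is about 0 to 7% in most settings. Anything larger needs screening pain to predict the outcome as well as pre-dose pain does, and also needs the two pre-dose scores to be only moderately correlated with each other. At the planned effect of 0.60, a gain of 3 to 4.5% in effective sample size is worth about one point of power. Any contribution from PUF is unquantified. The documents do not support a claim of a material loss of power or of a special problem in the 30-subject arms: at their planned effect of 0.75 those comparisons start slightly higher and gain a similar amount.

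**What to change.** Before the IDMC sees unblinded pain scores at about 90 subjects:

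- In Section 9.7.1.14 and the synopsis, specify the primary ANCOVA with site and treatment as factors and with pre-dose pain NRS, screening pain NRS and PUF total score as covariates.
- State that where screening and dosing fall on one day and only one pain NRS was recorded, that score is used for both.
- For SUID and the urgency-change endpoints, name the pre-dose and screening urgency NRS as covariates.
- Keep the pain intensity difference defined from the pre-dose score, so that the endpoint does not change.
- Carry the same wording into the separate SAP.

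The cost is two degrees of freedom in the primary model and one or two lines of text, with no new data.

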	
Primary Efficacy Determination: The primary efficacy endpoint will be compared between the URG101 and the lidocaine, heparin, and placebo groups using an analysis of covariance model which will include factors for treatment and baseline pain values. Pairwise comparisons of least squares means between URG101 and each of the other treatment arms will be performed. If the p-value associated with these comparisons is < 0.05 in favor of URG101, the primary aim of the trial will be confirmed.
 
Missing data for efficacy values will be imputed by the last observation carried forward method.
 
Secondary Efficacy Determinations: Analyses of secondary endpoints relating to changes in the NRSs for pain and urgency will be performed using analysis of covariance models similar to that used for the primary efficacy endpoint. Nonparametric methodology in exploratory analyses may be used to supplement the parametric analyses.
 
Treatment group comparisons relative to improvement on the PORIS questionnaire, (Question 3), will be made with standard contingency table techniques.
 
Pharmacokinetic Determinations: A comparison of pain and urgency assessments as measured by 11-point NRS to plasma lidocaine concentrations at 1 hour after study drug administration will be made for the PK set.

	
Safety Determinations: All safety analyses will be performed on the safety analysis set.
 
The change in INR and aPTT at baseline and 1 hour will be compared for the various treatment groups using descriptive statistics.
 
Other Determinations: Demographic and disposition data, randomization, drug administration, medical history, prior and concomitant medications, adverse events, clinical laboratory measurements, vital signs, physical examination findings, and all other safety data will be listed by subject and time point. Descriptive statistics will be tabulated for change from baseline in the vital signs. In addition to clinical and laboratory assessments, subject safety will be monitored by recording adverse events and serious adverse events throughout the study. Any pregnancy that occurs during the study will be promptly reported to the sponsor, but will not be considered a serious adverse event. Treatment-emergent adverse events will be summarized by type, frequency, severity, relationship to study drug, and number of subjects per treatment. Adverse events will be coded according to the Medical Dictionary for Regulatory Activities.

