9.1.6 Interim Study Analysis

After recruitment and treatment of the first ~90 (50%) of the planned 180 subjects, the IDMC will examine the conditional power and determine if a modification to the sample size up to 300 subjects is required to yield an overall power of 90%. An adjustment to the type 1 error rate will not be necessary if the conditional power is >39% at the interim assessment.

The IDMC will consist of 3 members: 1 physician expert in IC/BPS, 1 expert in clinical development, and a biostatistician. None of the IDMC members will be associated with study personnel; all communication between the IDMC and study personnel will be pre-defined and governed by the IDMC charter. The IDMC will have access to unblinded pain scores to perform their assessment of conditional power.

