9.2 DISCUSSION OF STUDY DESIGN INCLUDING CHOICE OF CONTROL GROUPS

The URG101 drug product contains the active ingredients, heparin and lidocaine, buffered to a pH of 7.4 (± 0.2). The anesthetic effect of lidocaine is anticipated to provide primary symptom relief of anesthetizing and “down-regulating” the bladder sensory nerves^{13,15,17,20}. Heparin is expected to potentiate this effect by coating the bladder epithelium and reducing the leak of additional potassium that would provoke

the nerves and initiate more symptoms. It is unlikely that heparin alone could provide much in the way of relief since the bladder sensory nerves would still remain “up-regulated” and volume sensitive even though the heparin would reduce the potassium leak. In a clinical trial that evaluated intravesical heparin, there was only minimal benefit, and most of the benefit of chronically administered heparin was after many months of use¹⁸. Therapeutic trials in this population are difficult to conduct due to recruitment issues. It has been shown that it can take more than 3 years to accrue 125 subjects with up to 10 active sites involved⁹.

A practical solution is proposed to evaluate the contribution of the components which is a four-arm study: (1) combination product, URG101, heparin-lidocaine buffered to pH 7.4 (\pm 0.2); (2) placebo [REDACTED] pH 7.4 [\pm 0.2]); (3) lidocaine buffered to pH 7.4 \pm 0.2; and (4) heparin buffered to pH 7.4 (\pm 0.2). Such a study would answer this critical question: Does heparin potentiate the lidocaine effect and justify the combination of the drugs?

Randomization will be used in this study to avoid bias in the assignment of subjects to treatment, to increase the likelihood that known and unknown subject attributes (e.g., demographics and baseline characteristics) are equal across treatment groups, and to ensure the validity of statistical comparisons across treatment groups. Blinding to treatment will be used to reduce potential bias during data collection and evaluation of endpoints.

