9.7.3 Determination of Sample Size

Sample size estimates were based on a pilot trial of heparin-lidocaine versus lidocaine alone and a prior two-arm study of URG101 versus placebo. The primary efficacy endpoint is SPID-12. The sample size calculation is based on a one-way analysis of variance, comparing SPID-12 from four treatment groups. A target sample size of approximately 180 subjects allocated among the four treatment groups. This sample size will be sufficient to achieve 90% power to detect a difference between the URG101 and components groups assuming a treatment effect size of 0.60. Once 50% of the subjects (90) have been enrolled, an unblinded interim assessment will be performed. The number of subjects for the study may be increased, based on the recommendation of the IDMC. Overall, a maximum of 300 subjects will be enrolled in Study URG101-105.

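### The primary success rule does not say whether all three comparisons must succeed, and the stated 90% power is per comparison: about 79% for all three at 180 subjects

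*Combined protocol and SAP*

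**What the plan says.** The synopsis (Primary Efficacy Determination) plans three tests from one analysis of covariance model: "Pairwise comparisons of least squares means between URG101 and each of the other treatment arms will be performed". Section 9.7.1.14 plans the same contrasts. Both places then give the same decision rule: "If the p-value associated with these comparisons is < 0.05 in favor of URG101, the primary aim of the trial will be confirmed". Section 9.7.1 sets the level: "All hypothesis tests will be 2-sided and will use an alpha level of 0.05". No order of testing or multiplicity procedure is given.

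Power is described in two places. The synopsis (Sample Size Estimate) says 180 subjects, split 60/60/30/30, are "sufficient to achieve 90% power to detect a difference between the URG101 and lidocaine groups assuming a treatment effect size of 0.60", and gives the same 90% for "URG101 and each of the placebo and heparin groups assuming an effect size for these comparisons of 0.75". Section 9.7.3 says the sample is "sufficient to achieve 90% power to detect a difference between the URG101 and components groups assuming a treatment effect size of 0.60". Both say the calculation rests on a one-way analysis of variance of the four groups.

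Section 9.1.6 asks the IDMC, after about 90 subjects, to "determine if a modification to the sample size up to 300 subjects is required to yield an overall power of 90" per cent. It does not say for which comparison or combination. Section 9.2 names the question the four-arm design must answer: "Does heparin potentiate the lidocaine effect and justify the combination of the drugs".

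**The concern.** The rule can be read as requiring all three tests to succeed or any one of them. The primary objective (8.1) lists the three comparators together, and the question in 9.2 can be answered yes only if URG101 beats lidocaine, so all three is the natural reading. It is not written down.

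The two readings have different consequences. If all three are required, type I error is controlled with each test at two-sided 0.05, but the chance of meeting the aim is lower than any single-comparison power. If any one were accepted, a trial in which heparin adds nothing to lidocaine could still confirm its primary aim through the heparin and placebo contrasts.

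The two power statements also disagree on heparin: 0.75 in the synopsis, 0.60 in 9.7.3, both with 90%. The heparin arm has only 30 subjects, so both cannot be right for the pairwise test.

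**Working it through.** **Inputs.** Group sizes are 60 URG101, 60 lidocaine, 30 heparin and 30 placebo (synopsis). The level is two-sided 0.05 (9.7.1), with success counted only in favour of URG101. No standard deviation is given, so the effect sizes d are taken as standardized differences. No dropout allowance is stated and none is applied. Residual degrees of freedom are 180 − 4 = 176.

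**Step 1: the plan's own figures.** The noncentrality is δ = d / √(1/n₁ + 1/n₂), and power comes from the noncentral t distribution.

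| URG101 versus | n | d | δ | Power |
|---|---|---|---|---|
| Lidocaine (both sections) | 60 v 60 | 0.60 | 0.60/0.1826 = 3.286 | 90.5% |
| Heparin or placebo (synopsis) | 60 v 30 | 0.75 | 0.75/0.2236 = 3.354 | 91.6% |
| Heparin (9.7.3) | 60 v 30 | 0.60 | 0.60/0.2236 = 2.683 | 76.1% |

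The synopsis figures reproduce as per-comparison power. The 9.7.3 figure does not reproduce for heparin: 60 versus 30 needs an effect of about 0.73 for 90%.

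**Step 2: power for all three.** The tests share the URG101 arm, so they are positively correlated:

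- lidocaine test with either 30-subject test: (1/60)/(0.1826 × 0.2236) = 0.408
- heparin test with placebo test: (1/60)/(0.2236²) = 0.333

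The trivariate normal probability that all three exceed 1.96 at the synopsis effects is 79.8%. Simulating the pooled-variance t tests (1,000,000 runs) gives about 79%.

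| Effects: lidocaine/heparin/placebo | All three, N = 180 | N for 90% on all three |
|---|---|---|
| 0.60/0.75/0.75 (synopsis) | 79% | about 228 (90.2%) |
| 0.60/0.60/0.75 (9.7.3 for heparin, synopsis for placebo) | 68% | about 288 (90.5%) |
| 0.60/0.60/0.60 | 59% | not reached at 300 (87.4%, normal approximation) |

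**Step 3: baseline adjustment.** The primary model includes baseline pain. If the effect sizes are unadjusted, they become d/√(1 − ρ²), where ρ is the baseline–outcome correlation. The documents do not give ρ. At the synopsis effects and 175 degrees of freedom:

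| Assumed ρ | 0.2 | 0.3 | 0.4 | 0.5 |
|---|---|---|---|---|
| All three | 81% | 84% | 88% | 92% |

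A site factor with 30 levels hardly matters: 79.2% at ρ = 0.

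**Step 4: if any one success were accepted.** With no true differences, the chance of at least one result in favour of URG101 is 6.6%, against 2.5% for a single test. If URG101 equals lidocaine and both are 0.75 SD better than heparin and placebo, the aim is confirmed 98% of the time, against 2.5% when all three are required.

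**The case against.** **The 90% in 9.7.3 may come from the omnibus test.** With all three controls 0.60 below URG101, the weighted grand mean is −0.60 × 120/180 = −0.40. The noncentrality is then 60 × 0.40² + 120 × 0.20² = 9.6 + 4.8 = 14.4, and the F test on 3 and 176 degrees of freedom has 89.8% power. This probably explains the figure. It does not rescue it, because 9.7.3 words it as power for URG101 against the components, and success is decided on pairwise contrasts.

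**79% is the low end with respect to baseline adjustment.** The sizing model has no covariate, so the effect sizes may well be unadjusted. That is fair, and the figure should carry its assumption. Dropout, also ignored, works the other way.

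**The 68% mixes two sections.** It does: 9.7.3 gives no placebo effect. It should be labelled as mixed.

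**The any-one reading is adopted nowhere.** True, and a separate analysis plan, to be finalized before database lock (9.7.1), could settle the rule. But the IDMC sees unblinded pain scores at about 90 subjects, so the rule should be fixed in the protocol before that look.

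**The synopsis claims no joint power, and the interim can raise the sample.** Also true: at 300 subjects, joint power at the synopsis effects is 97%. But the re-estimation aims at an overall power that is not tied to an event in the visible text. Part of 9.7.4 is redacted and may define it.

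**Conclusion.** The concern holds. The success rule is incomplete, and the stated power is not the power to meet the primary aim if all three comparisons must succeed. At 180 subjects, before any increase, the synopsis assumptions give about 79% for all three. This takes the effect sizes as applying to the primary model, with no dropout. If they are unadjusted, assumed baseline correlations of 0.2 to 0.5 give 81% to 92%. The claim in 9.7.3 conflicts with the synopsis and overstates the heparin comparison by about 14 percentage points (90 − 76). The 6.6% and 98% figures matter only if an any-one rule were applied. The design itself is sound; the defect lies in the decision rule and the power statement.

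**What to change.** 1. In the synopsis and 9.7.1.14, replace the decision sentence with: *The primary aim is confirmed only if URG101 is superior to lidocaine, to heparin and to placebo, each at two-sided 0.05, with no alpha adjustment.*
2. In the synopsis and 9.7.3, label the 90% as per comparison and add: *Power for all three comparisons at 180 subjects, before any sample size increase, is about 79%.* State whether the effect sizes are baseline-adjusted; if they are not, give the assumed correlation and the resulting power.
3. Reconcile the heparin effect size. Either use 0.75 in both places, or keep 0.60 and state about 76% for heparin and about 68% for all three with placebo at 0.75.
4. In 9.1.6, and in the synopsis text on the interim, say whether the 90% target means all three comparisons or URG101 against lidocaine. If the redacted interim text already says so, repeat it there.

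The cost is wording and a less favourable stated power; no extra patients are needed for that. Aiming for 90% on all three would take about 228 subjects at the synopsis effects, or about 288 at 0.60/0.60/0.75, both within the cap of 300. With 0.60 for all three comparisons, the cap would not be enough.
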